9.1.3 Study Measures

HMH Survey Administration: Parents will complete the baseline HMH survey at time of enrollment; parents will complete the abbreviated follow-up HMH survey at intervention completion (6-months). The HMH survey constitutes an abbreviated version of the Oncology EIS survey which has been utilized in two prior studies with high willingness to participate and low participant burden.^{10,17} Survey domains include: 1) Sociodemographics; 2) HMH (housing, transportation, utilities, food); 3) Finances; 4) Current resources; 5) Social supports; 5) Resilience; and 6) Anxiety. Survey administration takes approximately 10-15 minutes and may be conducted with an interpreter. Surveys are preferentially administered face-to-face (questions read-aloud by CRA) to overcome health literacy barriers which are of particular pertinence in the target patient population for this study. Surveys may be administered either on an iPad or paper/pencil. For two-parent households, while one parent consents to study participation and serves as the primary survey respondent (e.g. demographics) it is permissible for both parents to contribute information to questions on household material hardship and finances per family preference. All families will be contacted by email or telephone (per family preference) in the week prior to the 6-month follow-up survey to remind them of the upcoming survey time-point. Families will then complete the 6-month follow-up survey with the study CRA either in clinic or inpatient. For those families for whom in-person survey administration is infeasible surveys may be conducted by telephone, virtual platform, or self-completed hardcopy as needed.

Medical Record Abstraction: Child demographic and clinical data will be collected via systematic chart review by trained CRAs at the completion of study receipt (6-months) and entered into a REDCap database. Ten percent of records will be abstracted by a second CRA and discrepancies will be reviewed to clarify abstraction methods and adjudicated by the PI and site PI. Abstracted data elements will include but not be limited to age, diagnosis, cancer risk group or stage, treatment protocol, treatment elements (chemotherapy, surgery, radiation), hospital lengths of stay, emergency department visits and ICU stays during intervention.

9.2 Procedures for Assignment to Study Group:

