Enrolled participants will be randomized 1:1 by site to receive either the PediCARE intervention or UC for a duration of 6-months.

Participants will be randomly assigned to PediCARE or UC with a 1:1 allocation by site as per a computer-generated randomization sequence created by the study statistician. Sequences will be embedded in REDCap by informatics personnel. This approach to randomization will allow for real-time randomization of participants. Study personnel will not have access to the sequences. After randomization, participants and study team will be unblinded to group assignment as the intervention is not amenable to blinding.

9.3 Intervention Procedures:

The PediCARE study will pilot direct resource provision (groceries and transportation) to households of children newly diagnosed with cancer with a goal of reducing a concrete measure of poverty, household material hardship (HMH).

9.3.1 Usual Care (UC) Components (Control): UC psychosocial support in pediatric cancer is institution-specific but routinely includes (1) a psychosocial clinician available as part of the cancer care team; (2) social work screening for social and financial needs including such examples as insurance coverage and eligibility for Institutional, community or private cancer foundation supports; (3) social work assistance with applications on a case by case basis for insurance (i.e. Medicaid) and community/institutional/private financial supports; and (4) provision of parking vouchers and/or limited gift cards (e.g. cafeteria and hospital-retail food) when available.

9.3.2 PediCARE Intervention Components: PediCARE includes direct resource provision in two domains: Food and Transportation. Resource provision will be centrally administered by DFCI.

(1) **Food:** Families will receive a monthly pre-paid allocation of Instacart funds for grocery purchasing and delivery in a dollar amount adapted from the March 2018 U.S. Department of Agriculture's (USDA) Thrifty Food Plan (see Appendix B) for family size (e.g. family of 4 with two toddlers will receive \$640; cost range based on family sizes of 2-7 people and capped at 7 people). The Thrifty USDA Food Plan serves as the national standard for a nutritious diet at a minimal cost and is used as the basis for maximum SNAP benefit (e.g. food stamp) allotments, as such it represents a valid bench-mark for household food costs.

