- At study entry, the site CRA will assist families randomized to PediCARE in creation of an Instacart account for online grocery purchasing and delivery. Account creation requires

a name, email address, telephone number, home address for grocery delivery, and a credit card, debit card, or gift card

- Families will subsequently be provided a monthly pre-paid allocation of Instacart funds the beginning of each month of study participation. Families will choose and order groceries at their discretion over the course of the study.
- Other logistics: Instacart grocery ordering can be performed on any smartphone or computer with internet access. Any enrolled family without access to either a smartphone or computer will be provided with access to an iPad in clinic or while inpatient for ordering. Groceries can be ordered for same-day or future delivery. Families who live in ZIP codes where Instacart delivery is not available (approximately 15% of the U.S.) will be provided with an equivalent dollar amount grocery gift card to their local grocery store.

(2) Transportation: Families will be provided with the option of either 48 round-trip rides (96 legs) over the course of six months to use as needed each month using RideHealth or (b) gas cards and parking passes to support an estimated 8 clinic/hospital visits per month. The flexibility of choosing which direct transportation support will best facilitate a family's ability to bring their child to clinic or the hospital is based on qualitative parent feedback from the PediCARE pretest.

(a) Transportation will be provided via RideHealth, a company which provides a HIPAA-compliant digital platform to coordinate patient transportation utilizing Uber/Lyft and other commercial ride services, a web-based on-demand transportation platform. This platform allows for HIPAA-compliant account generation using PHI on the back-end, and then links to ride-scheduling with Uber/Lyft or other commercial drivers on the front-end without PHI. Built for healthcare, RideHealth allows ride-authorization for patients between specified sites (i.e. home and hospital/clinic). Rides are booked by the parent, and can be booked in advance (e.g. for a planned clinic visit or hospital stay) or on-demand 24-hours a day via their website or dedicated call center (e.g. for unplanned clinic or Emergency Department visits). RideHealth provides real-time analytics on utilization and performance including timeliness and cost.

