- At study entry, the lead-site CRA will create a RideHealth account for families randomized to PediCARE within the central DFCI RideHealth account. Families can view only their own information to facilitate ride requests. Each account will include pre-authorization for 48 round-trip rides (96 legs) over six months.
- The local site CRA will educate families on utilization of the RideHealth patient-facing app to request rides (process is similar to Uber/Lyft app for ride scheduling)
- Ride data including utilization, cost, and time will be provided to the lead site linked to study ID by RideHealth

(b) Families will be provided with gas cards in a dollar amount stratified by distance from hospital based on estimated average frequency of clinic visits/hospitalization and 2018 gas costs. Specifically, families who live <180 miles from the hospital will be provided with \$200/month in gas cards; those who live \geq 180 miles from the hospital will be provided with \$300/month in gas cards. Families will receive 8 parking passes per month at sites where families pay for parking.

PediCARE will provide both groceries and transportation support to all intervention recipients for the duration of the study. Pilot families will be randomized 1:1 at each site to receive the

PediCARE intervention or UC for 6-months which represents the most intensive phase of treatment for children with leukemia and neuroblastoma and covers the duration of chemotherapy treatment for most solid tumor and lymphoma diagnoses.

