16.0 Study Evaluations Table

	Intervention Group	Usual Care Group
Screening (HIPAA Waiver Requested)		
Diagnosis type/date	X*	X*
Date of Birth	X*	X*
Primary oncology team	X*	X*
Planned chemotherapy regimen	X*	X*
Primary language	X*	X*
Planned location of treatment	X*	X*
16-001 enrollment (DFCI only)	X*	X*
Sociodemographics	X	X
Following Informed Consent		
Baseline parent survey	X	X
Randomization	X	X
Remuneration		X
Each month on study		
Resource provision (PediCARE)	X	
Usual Care		X
End of study		
Follow-up parent survey	X	X
Remuneration	X	X
Clinical and treatment characteristics abstraction	X*	X*
Health Care Utilization Data Abstraction	X*	X*

* This item will be extracted from the child's medical record

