This follow-up survey takes about 10 minutes to complete and includes questions about housing, utilities (heat/electricity), food and income. We understand that some of these questions may feel personal and difficult to answer. You may skip any questions and even stop completing the survey at any time.

Survey responses will be kept confidential and not shared with your treatment team. No information will be presented in any way that would permit identification of your family or child.

A. Demographics

In the following questions we would like to ask you a bit about yourself and your family.

1. What is your relationship to the patient?
 - a. Mother
 - b. Father
 - c. Legal Guardian (please specify relationship): _____
 - d. Other Guardian (please specify): _____

2. How old are you?
 - a. Age in years: _____
 - b. Prefer not to answer

3. What is your child's current health insurance:
 - a. Private insurance
 - b. Medicaid Children's Health Insurance Program (CHIP) (public insurance)
 - c. Private insurance plus Medicaid/CHIP
 - d. Uninsured/Self-pay
 - e. Other (please specify; e.g. Military): _____

B. Housing and Transportation

The following questions apply to the home in which you and your child currently live and how you get to and from the doctor or hospital.

1. What is your zip code? _____
2. Please tell me what type of housing you and your child live in (choose the best response):
 - a. Apartment
 - b. House/Townhouse/Condo
 - c. Mobile home/trailer
 - d. Room/rented room
 - e. Shelter or transitional living situation
 - f. No steady place to sleep at night (e.g. temporarily staying with others, in a hotel, on the street, in the car, in a park, etc.)
 - g. Other (please specify): _____
3. Do you think you are at risk of becoming homeless?
 - a. Yes
 - b. No
4. How many people (including yourself and your child) are currently living in your home?
_____ Number of people
_____ Of these people, how many are children (<18 years old)?
_____ Of these people, how many are adults (>=18 years old)?
_____ Of the adults, how many bring income into the household?
5. How many bedrooms are in your home?
_____ # bedrooms
6. How many places have you and your child lived in the past year?
_____ # of places
7. During the past 6 months, was there a time when you were not able to pay the rent or mortgage on time because of financial difficulties?
 - a. Yes
 - b. No

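### ED and ICU use is counted only from the chart while PediCARE alone supplies study-paid transport, so visits elsewhere could be captured unequally by arm, in a direction and size the documents do not establish

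*Combined protocol and SAP*

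**What the plan says.** - **Source of the outcome.** Section 9.1.3 has research assistants review the chart at 6 months; the utilization elements are "hospital lengths of stay, emergency department visits and ICU stays during intervention". In section 16.0 the utilization row carries, for both arms, the footnote "This item will be extracted from the child's medical record". The documents mention no outside-hospital records or claims data, and give no rule on which facilities count.
- **Surveys.** The introduction to the follow-up survey in Appendix B says that it "includes questions about housing, utilities (heat/electricity), food and income". No item in either the baseline or the follow-up survey asks about ED or ICU care at any hospital.
- **Transport under PediCARE (section 9.3.2).** "RideHealth allows ride-authorization for patients between specified sites (i.e. home and hospital/clinic"). Rides may be booked ahead or "on-demand 24-hours a day via their website or dedicated call center (e.g. for unplanned clinic or Emergency Department visits"). A family may choose the other option: "Families will be provided with gas cards in a dollar amount stratified by distance from hospital", split at 180 miles, with parking passes at sites that charge for parking.
- **Transport under usual care (section 9.3.1).** The list includes "provision of parking vouchers and/or limited gift cards (e.g. cafeteria and hospital-retail food) when available", and social-work help with applications for insurance and other support. It includes no study-paid rides.
- **Use of the outcome.** Section 11.0 estimates the share of patients with any ED or ICU visit in each arm and the between-arm difference, with a 90% interval. Section 2.2 expects a lower share with PediCARE. Section 8.2 says the secondary endpoints are to inform the size of effect for a later trial.

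**The concern.** The intervention acts on access to the place where the outcome is recorded. A PediCARE family can take a paid ride to the study hospital at any hour. A usual-care family without reliable transport, or living far away, may go to a nearer ED, and the plan does not say whether that visit would be found. The population is sensitive to this: transportation insecurity is one of the four qualifying hardships (section 3.1), and the 180-mile gas-card band shows that distant families are expected.

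Randomization does not protect against this, because the difference arises after assignment. Nor does the double abstraction of 10% of records in section 9.1.3, which tests agreement between abstractors and cannot find visits that never entered the chart. At stake is the utilization estimate that the next trial would be planned on. It could be shrunk, reversed or exaggerated by where care was sought rather than by how much was needed. The primary feasibility endpoint is untouched.

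**Working it through.** The plan gives no ED/ICU rate, target effect or chart capture rate, so there is no figure of its own to reproduce. The calculation shows only what unequal capture would do under stated assumptions.

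**Inputs from the documents.** 14 + 6 = 20 families per arm (section 4.0); 90% confidence level (section 11.0).

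**Assumptions, not from the documents.** The true share p with any visit is 40% or 60%, the same in both arms. The share missed, m, is 10% in PediCARE and 20% or 30% in usual care.

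**Step 1: misses counted per patient.** Observed share = p × (1 − m).

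| True p | PediCARE, 10% missed | Usual care, 20% missed | False difference | Usual care, 30% missed | False difference |
|---|---|---|---|---|---|
| 40% | 36% | 32% | +4 points | 28% | +8 points |
| 60% | 54% | 48% | +6 points | 42% | +12 points |

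**Step 2: misses counted per visit.** The endpoint is any visit, so a child with several visits is misclassified only if all are missed. With Poisson visits, the mean is λ = −ln(1 − p), and observed share = 1 − exp(−λ(1 − m)).

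| True p | λ | PediCARE, 10% missed | Usual care, 20% missed | False difference | Usual care, 30% missed | False difference |
|---|---|---|---|---|---|---|
| 40% | 0.511 | 36.9% | 33.6% | +3.3 points | 30.1% | +6.8 points |
| 60% | 0.916 | 56.2% | 52.0% | +4.2 points | 47.3% | +8.8 points |

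Across both steps the false difference is roughly 3 to 12 points.

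**Step 3: random error in this pilot.** The 90% Wald half-width of the difference is 1.645 × √(2p(1 − p)/20). At p = 40% or 60% it is 25.5 points; at p = 50% it is 26.0 points. The artefact is smaller than this. The half-width shrinks as n grows; the artefact does not, because n does not enter steps 1 and 2.

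**Step 4: dependence on the assumed direction.** Suppose a true benefit of 40% against 60% (−20 points), with per-patient misses:

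- 10% missed in PediCARE, 20% in usual care: 36% − 48% = −12 points.
- 10% and 30%: 36% − 42% = −6 points.
- 10% in both arms: 36% − 54% = −18 points, a proportional shrinkage only.
- 30% in PediCARE, 10% in usual care: 28% − 54% = −26 points, an exaggerated benefit.

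**The case against.** A reader might infer that the plan will understate PediCARE's benefit. The documents do not support that, for four reasons.

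1. The pull toward the study hospital is weakest for the families it matters most for. The distance bands belong to the gas-card option, and gas cards are tied to no destination; they could pay for a trip to a local ED. Only the parking passes are tied to study sites. The share choosing rides is not given.
2. Usual care is not without transport help. It can offer parking vouchers and help with insurance applications, and both surveys list a Medicaid transportation benefit among the ways to reach care.
3. A chart review is not necessarily limited to study-hospital visits. These children are to receive chemotherapy at the study site, so outside care may reach the chart, and an ICU stay probably more often than an ED visit (a judgement). The abstraction form and the Ride Health sheet were not available to check.
4. The direction in steps 1 and 2 is an input. Easier transport could also truly raise ED attendance, which would be an effect of the intervention and not a measurement error.

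All four stand, and they remove any claim to a known direction or size. It is also fair that this is a secondary endpoint in a 40-family pilot, and that the next trial can set its own rules for finding visits. What survives is that the plan has no way to tell whether capture differs by arm, although it intends to use the between-arm difference for planning.

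A reader might also infer that parent report should become part of the main endpoint. That would bring its own bias: parents know their arm (section 9.2), recall is imperfect, and families who return no survey would have chart data only. Section 8.1 tolerates 20% attrition per arm, and section 11.0 accepts 28 of 40 with complete data, so unequal survey return could itself make capture differ by arm.

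**Conclusion.** The concern holds in a limited form. Chart abstraction is the only source for ED and ICU use, no survey item covers care at other hospitals, and study-paid transport goes to one arm. Unequal capture is therefore possible and would go undetected. Under-counting in usual care is plausible but not established. The 3 to 12 points rest wholly on the assumed true shares (40–60%) and miss rates (20% against 10%, up to 30% against 10%). Such a bias would be hidden within this pilot's random error of about 25 to 26 points, but would persist in a larger trial that measured visits the same way. The change is a cheap improvement to a secondary outcome and does not call the primary analysis into question.

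**What to change.** - Add one identical item to the 6-month survey in both arms: whether the child was seen in an ED or admitted to an ICU at any hospital during the 6 months on study, how many times, and where.
- Have abstractors record study-site visits and outside visits noted in the chart separately, and state in section 9.1.3 that both are recorded.
- Keep the chart-based proportion as the main secondary result. As a supplementary sensitivity analysis among survey completers, report by arm the proportion from chart plus parent report, with the chart-only proportion in the same families and the number of visits found only by parent report. That last number tells the next trial how often charts miss visits in each arm.

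The cost is one question in a survey of about 10 minutes and one extra field on the abstraction form, with no new visit and no larger sample. The downside is parent recall, unblinded reporting and survey non-completion, which is why the supplementary result should not replace the chart-based one.

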10.0 Data Management and Confidentiality

10.1 HIPAA Authorization and Waivers: The following protected health information (PHI) is needed to carry out the study: contact information (names, addresses, phone numbers, and email address) necessary to identify subjects, ask for consent, and ensure follow-up contact with subjects throughout the study; medical record numbers are needed to abstract medical information; child date of birth and diagnosis, necessary to calculate the child's age and time passed since diagnosis; parent date of birth, necessary to calculate parent age. PHI data will be stored in a HIPAA compliant REDCap database accessible only to the study team, all of whom have HIPAA Certification and have completed the training mandated by the DFCI Institutional Review Board.

A HIPAA Waiver of Authorization will be requested to enable thorough screening for eligibility. This process involves no more than a minimal risk to subjects' privacy because identifiers will be collected in a secure way and destroyed after the study is closed. In addition, the protected health information collected will not be reused or disclosed to any other person or entity other than the research team, except as required by law. Because we aim to enroll participants as close to the time of cancer diagnosis as possible, we have a relatively narrow window in which to identify eligible participants. Without such a waiver, we would have to rely solely on provider-generated referrals or patient and parent self-referral, which would add an undue burden to oncology providers and potentially lead to such slow participant accrual that the research would be rendered infeasible. Alternatively, requesting consent from each potential study participant prior to review of preliminary eligibility would result in an unnecessary burden for families.

10.2 Data Management: All information collected for research purposes will be de-identified prior to analysis.

- Identifying information will include data (names, addresses, phone numbers, emails) necessary to identify subjects initially to ask for consent as well as to contact for follow-up survey administration if necessary; child's demographic and disease information.
- The data will be coded, databases secured with a password, and contact information and medical record numbers will be kept in a separate database accessible only to the Principal Investigator and local RA who have both undergone HIPAA Certification and the training mandated by the IRB. Study databases will not contain identifying information, and will be linked to identifying information by a unique study ID.
- A separate password-protected key file containing the link between identifying information and research data will be maintained by the PI behind the DF/HCC firewall. We have extensive experience in maintaining confidentiality utilizing these methods.

10.3 Use of Data for Intervention Administration for Parents receiving PediCARE:

- Per the Business Agreement, parent contact information (specifically email address and home address) with study ID number will be utilized for creation of a RideHealth account which provides HIPAA compliant privacy protections.

- Parents will create their own Instacart account which will not be linked to study ID and to which research team will not have access. Parent email address will be utilized to send an Instacart gift card for each month of the intervention.

